	> 30 minutes	4			
3	No	0	x	0.25 (0.25 Den)	
	Yes	1			
4	No	0	x	0.30 (0.30 Den)	
	Yes	1			
5	No	0	x	0.20 (0.20 Den)	
	Yes	1			
6	No	0	x	0.31 (0.31 Den)	
	Yes	1			
TOTAL =				Denominator (Sum Den)	Raw Score

$$\text{Normalized HHT-ESS} = \left[\frac{\text{Raw Score}}{\text{Denominator (2.71)}} \right] \times 10$$

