The mechanisms of action, published literature, and results of an unpublished study presented at the 13th HHT International Scientific Conference suggest a role of β -blockers in the management of HHT-associated epistaxis. The work by Mei-Zahav et al suggest propranolol gel may be an effective treatment for HHT-associated epistaxis. However, intranasal propranolol is not well tolerated and is associated with arrested cilia movement. Topical timolol has advantages over propranolol in that it is well-tolerated and has been shown to not have an effect on nasal mucosa.(Jagdale, Shewale, and Kuchekar 2016) Patients with certain pre-existing heart conditions or metabolizing variants of the liver enzyme CYP2D6 are at increased risk for adverse effects of timolol ophthalmological solution.

Given our understanding of the pathophysiology of HHT-associated epistaxis, mechanism of action, and pharmacokinetics of intranasal timolol, we believe it is now appropriate to conduct a Phase II double-blinded, placebo controlled randomized clinical trial to evaluate the efficacy of intranasal timolol gel. The results of this Phase II study will provide additional information on the benefits and risks of intranasal timolol, which can be used to inform the design of a definitive Phase III study.

VI. SPECIFIC AIMS

The Specific Aims are to determine in adults with HHT-associated epistaxis:

1. If topical timolol gel is more effective than placebo in reducing the frequency and severity of epistaxis.
2. If topical timolol gel is more effective than placebo in improving hemoglobin levels.
3. The frequency of adverse events, side effects, and safety profile of topical timolol gel delivered to the nasal mucosa, and safety profile of topical timolol gel delivered to the nasal mucosa of HHT patients.

VII. DESIGN PLAN

Study Type

The study will be a multi-site, double-blind, placebo-controlled randomized clinical trial performed at two tertiary academic medical center HHT Centers of Excellence.

Blinding

Research participants and the members of the investigative team who will have direct subject interaction will be blinded to treatment assignment. The research statistician, [name], will not be blinded. All subject assessments will be performed without knowledge of treatment.

Study Population

Inclusion Criteria:

- 1) Adults ages 18 and older
- 2) Confirmed clinical (meeting at least 3 of the 4 Curaçao Criteria) or genetic diagnosis of HHT

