- 3) *Epistaxis Severity Score (ESS) ≥ 4 and 2 or more nosebleeds per week with a cumulative nosebleed duration of at least 5 minutes per week*
- 4) Stable nasal hygiene and medical regimen for preceding 1 month
- 5) Stable epistaxis pattern over the preceding 3 months

Exclusion Criteria:

- 1) Contraindications for systemic β adrenergic blocker administration
 - a. Hypersensitivity to β adrenergic blockers
 - b. Asthma or bronchospasm
 - c. Congestive heart failure with LVEF <40%
 - d. Hereditary pulmonary arterial hypertension
 - e. Baseline bradycardia (HR <55 beats per minute)
 - f. Sick Sinus Syndrome
 - g. 2nd or 3rd degree heart block, left or right bundle branch block, or bifascicular block
 - h. Uncontrolled diabetes mellitus (most recent HbA1c >9%) or diabetic ketoacidosis within last 6 months
 - i. Hypotension (systolic blood pressure < 90)
- 2) Known hypersensitivity to timolol
- 3) Severe peripheral circulatory disturbances (Raynaud phenomenon)
- 4) Known intermediate or poor metabolizer variant of the liver enzyme CYP2D6
- 5) Current use of any of the following known strong CYP2D6 inhibitors: fluoxetine (Prozac), paroxetine (Paxil), bupropion (Wellbutrin), quinidine, quinine, ritonavir (Norvir), and terbinafine (Lamisil)
- 6) Current use of the following other drugs known to pharmacodynamically interact with timolol: diltiazem, verapamil, digoxin, digitalis, propafenone, disopyramide, clonidine, flecainide, or lidocaine
- 7) Patients currently treated or who plan to initiate treatment with β -blockers
- 8) Use of any anti-angiogenic medication in the last month prior to recruitment, including bevacizumab, pazopanib, thalidomide, or lenalidomide
- 9) Illicit drug use, except marijuana
- 10) Known pheochromocytoma
- 11) Use of anticoagulants, antiplatelet, or fibrinolytic therapies within the last month prior to recruitment, except for low-dose (81 mg or less) of aspirin
- 12) Pregnancy or planned pregnancy in the next 6 months or currently breastfeeding
- 13) Inability to read or understand English

- 14) Inability to complete 8 weeks of therapy for any reason

Eligibility Determination

To determine potential eligibility for the study, the research team will query the medical record based on the following inclusion/exclusion criteria:

- Age (18 years or older)
- Medication history to assess current use of a β -blocker (exclusion)
- Allergy history to timolol (exclusion)
- Changes in epistaxis care in the last month (exclusion)

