Assisted Epistaxis Severity Score (aESS). Assessment of epistaxis severity will be obtained by the validated instrument, the *Epistaxis Severity Score (ESS)*. (Hoag et al. 2010) (Appendix 1) To complete the *ESS*, patients are asked to consider typical symptoms over the previous 3 months. However, with the 8-week duration of our trial, patients will complete the *aESS* in reference to their epistaxis over the past 1 month. The *ESS* contains 6 items – frequency, duration, and intensity of nosebleeds, whether patient has

sought medication attention, whether patient is anemic, and whether patient has received a blood transfusion. The overall score ranges from 0 to 10, with severity of nosebleed based on score graded as *None* composite score of 0-1, *Mild* 1-4, *Moderate* 4-7, and *Severe* as 7-10. The minimal important difference noticeable by both patients and clinicians in the ESS scoring system is estimated as a change of 0.71. (Yin et al. 2016)

HHT Endoscopy Score (HES). The *HHT Endoscopy Score (HES)* is an endoscopy staging score developed as a way to quantify the severity of the patient's nasal telangiectasias as seen on physical exam. (Reh et al. 2014) The *HES* was shown to correlate with the *ESS*. Its parameters are telangiectasia sites, patterns, crusting, location, perforation, density, and relative AVMs. Scoring of the HES is illustrated in Appendix 2.

Epistaxis-Specific Quality-Of-Life Questionnaire (EQQoL). The EQQoL measures 13 items that focus on the impact of epistaxis on the patient's physical, functional, and emotional status and quality of life. (Ingrand et al. 2011) The EQQoL was shown to have satisfactory psychometric properties and when combined with the SF-36 measures both disease-specific and general quality of life. See Appendix 3 for questionnaire.

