Secondary Outcomes:

- 1) Clinical Global Impression – Improvement (CGI-I) Score
- 2) Mean change in hemoglobin
- 3) Change in intensity of telangiectasias in the nasal mucosa as determined by the HHT endoscopic scale (HES)

Summary of Project Design

VIII. SAMPLE SIZE AND PLANNED STATISTICAL ANALYSIS

Sample Size

Sample size estimate for the proposed study were derived from the single study(Ichimura et al. 2016) of within subject change in severity of epistaxis associated with timolol ophthalmic solution (0.5%) as a nasal drop. In that study, 9 of the 11 subjects (82%) experienced a reduction in the severity of bleeds as measured on a 5-point Likert scale. We hypothesize a similar response (82%) in our proposed study among subjects randomized to receive timolol gel and a 20% response rate among subjects randomized to placebo gel, corresponding to a difference of 62%.

A power analysis was performed using Fisher’s exact test in G-Power 3.1.2. We estimate that a total sample size of 24 patients (ie., 12 in each arm) is needed to allow us to detect with 80% power at the 2-sided alpha level of 0.05 a difference of 62% or more in the percent of subjects who experience reduction of severity of

bleeds between treatment groups. Considering a 20% drop out rate, we plan to enroll 30 subjects in the study.

Statistical Analysis

Standard descriptive statistics will be used to describe distribution of baseline characteristics in each of the study groups. The effect of the intervention will be measured as the difference in the within-subject change (baseline – 8-week follow-up) in *ESS* scores between the two treatment groups calculated as shown below.

1) Within subject difference with each treatment group

$$\begin{aligned}\Delta ESS_{\text{Timolol}} &= (ESS_{\text{Timolol_base}} - ESS_{\text{Timolol_8-Week}}) \\ \Delta ESS_{\text{Control}} &= (ESS_{\text{Timolol_base}} - ESS_{\text{Timolol_8-Week}})\end{aligned}$$

2) Between treatment difference

$$\Delta ESS_{\text{Timolol}} - \Delta ESS_{\text{Control}}$$

The 95%CI around this effect size will be determined to assess the precision of the observed effect and whether a clinically meaningful difference is plausible given the observed results.

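### Appendix 1 contradicts itself on the primary-endpoint score: the ESS item denominators sum to 2.76, but the normalizing formula divides by 2.71, so the maximum is 10.18, not 10

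*Combined protocol and SAP*

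**What the plan says.** Appendix 1 gives each of the six ESS items a coefficient and, in brackets, a denominator: 0.70, 1.00, 0.25, 0.30, 0.20 and 0.31. The total row names the divisor "Denominator (Sum Den", that is, the sum of these denominators. The displayed formula then divides the raw score by "Denominator (2.71" and multiplies by 10.

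Section VII, Variables Under Study, says of the ESS: "The overall score ranges from 0 to 10". It gives the minimal important difference as "estimated as a change of 0.71".

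The score has two uses. Change in ESS from baseline to 8 weeks is the primary outcome (sections VII and VIII). An ESS of at least 4 is an entry criterion, alongside "2 or more nosebleeds per week" and a cumulative bleeding time of at least 5 minutes a week (section VII, Inclusion Criteria). The trial is to be "performed at two tertiary academic medical center HHT Centers of Excellence".

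**The concern.** A scorer who follows the total row divides by 2.76; one who follows the formula divides by 2.71. The two instructions sit next to each other and no other scoring rule is given. Only one of them is compatible with the stated 0 to 10 range.

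Three things depend on the scale: the size of the treatment difference and its confidence interval, entry at a threshold of 4, and the comparison with 0.71. Section VIII intends to judge "whether a clinically meaningful difference is plausible given the observed results", and the 0.71 benchmark is quoted for the ESS as an instrument, so the score computed here should be that instrument's score.

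**Working it through.** **1. Sum of the denominators (inputs from Appendix 1).**

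| Item | Coefficient | Highest code | Product | Printed denominator |
|---|---|---|---|---|
| 1 Frequency | 0.14 | 5 | 0.70 | 0.70 |
| 2 Duration | 0.25 | 4 | 1.00 | 1.00 |
| 3 Intensity | 0.25 | 1 | 0.25 | 0.25 |
| 4 Medical attention | 0.30 | 1 | 0.30 | 0.30 |
| 5 Anemia | 0.20 | 1 | 0.20 | 0.20 |
| 6 Transfusion | 0.31 | 1 | 0.31 | 0.31 |
| Sum | | | 2.76 | 2.76 |

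The plan's 2.71 is not reproduced. Every denominator equals its coefficient times its highest code, and no subset of the six sums to 2.71.

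**2. Maximum score.** With 2.71: 2.76 / 2.71 × 10 = 10.18. With 2.76: exactly 10. Of the 6 × 5 × 2 × 2 × 2 × 2 = 480 answer patterns, one (all items at maximum) exceeds 10 under 2.71.

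**3. Consistent use of 2.71 where 2.76 is meant.** Every score is multiplied by 2.76 / 2.71 = 1.0185, an excess of 1.85%.
- Treatment difference: taking 1.55 points for illustration (the between-arm difference reported for the propranolol gel trial in section V), 1.55 × 2.71 / 2.76 = 1.52.
- t-test: the mean difference and its standard error are multiplied by the same constant, so the t statistic and p-value do not change. The confidence limits scale by the same 1.85%.
- Benchmark: a change of 0.71 on the 2.76 scale would be recorded as 0.71 × 1.0185 = 0.723.

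**4. Entry threshold.** ESS 4 corresponds to a raw score of 1.084 under 2.71 and 1.104 under 2.76. Five of the 480 patterns fall on different sides, all with raw score 1.09 (4.02 against 3.95). None has the several-per-week frequency answer or higher. Two have once per month, which does not fit the bleed-count criterion. Three have once per week; as codes for items 1 to 6:
- (2,1,1,0,0,1) and (2,2,0,0,0,1): transfusion for nose bleeding, but medical attention never sought, which is hardly coherent.
- (2,0,0,1,1,1): typical bleeds under 1 minute. Two such bleeds total under 2 minutes a week, so the 5-minute criterion would almost certainly fail.

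These are unweighted counts of patterns, not probabilities for patients.

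**5. Contingency: baseline scored with 2.71, follow-up with 2.76, in both arms.** A patient's change shifts by follow-up score × (1 − 2.71/2.76) = follow-up score × 0.0181:
- score 4: 0.07
- score 7: 0.13
- score 10.18: 0.18

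The between-arm contrast shifts only by 0.0181 times the between-arm difference in follow-up means. For an assumed 1.55 points that is 1.55 × 0.0181 = 0.03.

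**6. Contingency: an item weight is wrong.** The gap is 2.76 − 2.71 = 0.05, so lowering any one denominator by 0.05 would give 2.71. Scores could then differ by up to 0.05 / 2.71 × 10 = 0.18 points, not proportionally, and the p-value need not be preserved. This requires a coefficient and its own denominator to be wrong together.

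**The case against.** The strongest reply is that 2.71 may be the instrument's own constant, obtained from unrounded coefficients. If the denominators were computed from coefficients already rounded to two decimals, the true sum could lie anywhere in 2.76 ± 13 × 0.005, that is 2.695 to 2.825, which includes 2.71. If instead the six denominators are themselves rounded values, the range is 2.76 ± 6 × 0.005, that is 2.73 to 2.79, which excludes it. The possibility stands. In that case no score changes, but the label and the stated range are still wrong. It is also fair that 2.71 appears once, in a displayed formula read from a PDF, so the page itself should be checked.

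A second reply is that a scorer would simply use the printed constant. The plan does not say that sites score separately or that the ESS is scored in an electronic tool; the app and the REDCap survey are described for daily logs. Mixing of divisors is therefore only a contingency.

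A reader might infer from the 0.18-point figure that the primary result could be off by that much. It is a maximum for one patient's change; a shift common to both arms largely cancels, and nothing suggests that the divisor would differ by arm. A reader might also infer that patients would be misclassified as responders at 0.71, but sections VIII and the primary outcome plan a mean difference with a confidence interval and no such classification.

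**Conclusion.** The contradiction is real and the scoring guide is wrong as written: 2.76 by its own label, 2.71 by its formula, and a maximum of 10.18 against a stated 10. Because every denominator agrees with its coefficient, the likelier error is the divisor, or else the label and range; a wrong weight is less likely. The documents alone cannot decide.

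The consequence is minor. On the assumption that 2.76 is meant and 2.71 is used throughout, estimates and confidence limits are 1.85% too large, the p-value is unchanged and eligibility is practically unaffected. On the assumption of a baseline/follow-up mix in both arms, the treatment contrast moves by about 0.03 points when follow-up means differ by 1.55. The documents do not support a reading that the primary comparison or the enrolled population would be materially distorted.

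**What to change.** Before any scoring, check the six coefficients and the divisor against the ESS source, and the printed 2.71 against the original page.
- If 2.71 is a misprint, divide by 2.76.
- If the source uses 2.71, keep it, and correct the sum label and the 0 to 10 range.
- If a weight is misprinted, correct the coefficient and its denominator together.

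State that this one version applies to eligibility and outcome at both sites and both visits. The cost is one check and a few corrected lines; design, sample size and data collection do not change.

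Separate editorial note: in section VIII, the line defining the control-arm change carries timolol subscripts. The lead-in, "scores between the two treatment groups calculated as shown below", the control label on the left-hand side and the second step make the intended contrast clear, so no result is affected. The subscripts should read Control for baseline and 8 weeks.

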Appendix 2.

Scoring of the *HHT Endoscopic Scoring System (HES)*.

	Endoscopic staging system score			
	0	1	2	3
Sites	1	2-3	4-5	≥6
Patterns	Punctuate	Interconnected	AVMs	
Crusting	None	Mild	Moderate/severe	
Location	Anterior septum	Inferior turbinate	Middle turbinate	Posterior septum
Perforation	No	Yes		
Density	>10 mm	5-10 mm	2-4 mm	<1 mm
Relative AVMs	None	<25%	25-50%	>50%

Appendix 3. Epistaxis-Specific Quality-of-Life Questionnaire (EQQoL)

Epistaxis-Specific Quality-of-Life Questionnaire (EQQoL)

Patient ID _____ Date _____

Please fill out the following survey that measures the burden of your nose bleeds upon your life.

- 1 = All the time
- 2 = Usually (About 90% of the time)
- 3 = Frequently (About 70% of the time)
- 4 = Sometimes (About 50% of the time)
- 5 = Occasionally (About 30% of the time)
- 6 = Rarely (Less than 10% of the time)
- 7 = Very rarely or never

1) Have you ever felt bothered by having a blocked-up nose?	1	2	3	4	5	6	7
2) Have you felt restricted by the weather or had to avoid going outdoors because of your nose bleeds?	1	2	3	4	5	6	7
3) Have you felt frustrated because your nose bleeds have stopped you doing what you wanted?	1	2	3	4	5	6	7
4) Have you been bothered by the presence of crusts in your nose?	1	2	3	4	5	6	7
5) Have you ever been afraid you could not stop a nose bleed?	1	2	3	4	5	6	7
6) Have you been tired or breathless because of your nose bleeds?	1	2	3	4	5	6	7
7) Have you taken any precautions to prevent your nose bleeds?	1	2	3	4	5	6	7
8) Have you ever spent a bad night because of your nose bleeds?	1	2	3	4	5	6	7
9) Have you ever been anxious because you have nose bleeds?	1	2	3	4	5	6	7
10) Do your nose bleeds restrict your relationships with friends or family?	1	2	3	4	5	6	7
11) Have your nose bleeds created problems with your work?	1	2	3	4	5	6	7
12) Have your nose bleeds restricted your leisure activities?	1	2	3	4	5	6	7
13) Have your nose bleeds restricted your mental activities?	1	2	3	4	5	6	7

Appendix 4.

SF-36: Accessible at https://www.rand.org/health-care/surveys_tools/mos/36-item-short-form/survey-instrument.html

Patient ID _____ Date _____

RAND > RAND Health > Surveys > RAND Medical Outcomes Study > 36-Item Short Form Survey (SF-36) >

36- Item Short Form Survey Instrument (SF-36)

RAND 36-Item Health Survey 1.0 Questionnaire Items

Choose one option for each questionnaire item.

1. In general, would you say your health is:

- 1 - Excellent
 - 2 - Very good
 - 3 - Good
 - 4 - Fair
 - 5 - Poor
-

2. **Compared to one year ago**, how would you rate your health in general **now**?

- 1 - Much better now than one year ago
- 2 - Somewhat better now than one year ago
- 3 - About the same
- 4 - Somewhat worse now than one year ago
- 5 - Much worse now than one year ago

The following items are about activities you might do during a typical day. Does **your health now limit you** in these activities? If so, how much?

	Yes, limited a lot	Yes, limited a little	No, not limited at all
3. Vigorous activities , such as running, lifting heavy objects, participating in strenuous sports	 1	 2	 3
4. Moderate activities , such as moving a table, pushing a vacuum cleaner, bowling, or playing golf	 1	 2	 3
5. Lifting or carrying groceries	 1	 2	 3
6. Climbing several flights of stairs	 1	 2	 3
7. Climbing one flight of stairs	 1	 2	 3
8. Bending, kneeling, or stooping	 1	 2	 3
9. Walking more than a mile	 1	 2	 3
10. Walking several blocks	 1	 2	 3
11. Walking one block	 1	 2	 3
12. Bathing or dressing yourself	1	2	3

During the **past 4 weeks**, have you had any of the following problems with your work or other regular daily activities **as a result of your physical health**?

- | | Yes | No |
|---|-----------------------|-----------------------|
| 13. Cut down the amount of time you spent on work or other activities |  |  |
| | 1 | 2 |
| 14. Accomplished less than you would like |  |  |
| | 1 | 2 |
| 15. Were limited in the kind of work or other activities |  |  |
| | 1 | 2 |
| 16. Had difficulty performing the work or other activities (for example, it took extra effort) |  |  |
| | 1 | 2 |
-

During the **past 4 weeks**, have you had any of the following problems with your work or other regular daily activities **as a result of any emotional problems** (such as feeling depressed or anxious)?

- | | Yes | No |
|--|-------------------------|-------------------------|
| 17. Cut down the amount of time you spent on work or other activities |  1 |  2 |
| 18. Accomplished less than you would like |  1 |  2 |
| 19. Didn't do work or other activities as carefully as usual |  1 |  2 |
-

20. During the **past 4 weeks**, to what extent has your physical health or emotional problems interfered with your normal social activities with family, friends, neighbors, or groups?

- 1 - Not at all
- 2 - Slightly
- 3 - Moderately
- 4 - Quite a bit
- 5 - Extremely

21. How much **bodily** pain have you had during the **past 4 weeks**?

- 1 - None
 - 2 - Very mild
 - 3 - Mild
 - 4 - Moderate
 - 5 - Severe
 - 6 - Very severe
-

22. During the **past 4 weeks**, how much did **pain** interfere with your normal work (including both work outside the home and housework)?

- 1 - Not at all
 - 2 - A little bit
 - 3 - Moderately
 - 4 - Quite a bit
 - 5 - Extremely
-

These questions are about how you feel and how things have been with you **during the past 4 weeks**. For each question, please give the one answer that comes closest to the way you have been feeling.

How much of the time during the **past 4 weeks**...

- | | All of the time | Most of the time | A good bit of the time | Some of the time | A little of the time | None of the time |
|---|-------------------------|-------------------------|-------------------------|-------------------------|-------------------------|-------------------------|
| 23. Did you feel full of pep? |  1 |  2 |  3 |  4 |  5 |  6 |
| 24. Have you been a very nervous person? |  1 |  2 |  3 |  4 |  5 |  6 |
| 25. Have you felt so down in the dumps that nothing could cheer you up? |  1 |  2 |  3 |  4 |  5 |  6 |
| 26. Have you felt calm and peaceful? |  1 |  2 |  3 |  4 |  5 |  6 |
| 27. Did you have a lot of energy? |  1 |  2 |  3 |  4 |  5 |  6 |
| 28. Have you felt downhearted and blue? |  1 |  2 |  3 |  4 |  5 |  6 |
| 29. Did you feel worn out? |  1 |  2 |  3 |  4 |  5 |  6 |
| 30. Have you been a happy person? |  1 |  2 |  3 |  4 |  5 |  6 |
| 31. Did you feel tired? |  1 |  2 |  3 |  4 |  5 |  6 |

32. During the **past 4 weeks**, how much of the time has **your physical health or emotional problems** interfered with your social activities (like visiting with friends, relatives, etc.)?

- 1 - All of the time
- 2 - Most of the time
- 3 - Some of the time
- 4 - A little of the time
-

5 - None of the time

How TRUE or FALSE is **each** of the following statements for you.

	Definitely true	Mostly true	Don't know	Mostly false	Definitely false
33. I seem to get sick a little easier than other people	 1	 2	 3	 4	 5
34. I am as healthy as anybody I know	 1	 2	 3	 4	 5
35. I expect my health to get worse	 1	 2	 3	 4	 5
36. My health is excellent	 1	 2	 3	 4	 5

ABOUT

The RAND Corporation is a research organization that develops solutions to public policy challenges to help make communities throughout the world safer and more secure, healthier and more prosperous. RAND is nonprofit, nonpartisan, and committed to the public interest.

[name]

[name]

RAND® is a registered trademark. Copyright © 1994-2016 RAND Corporation.

